### **Safety outcomes (Appendix 2):**

- ART toxicity
- ART simplification (change in ART regimen from initiation to ART regimen with fewer pills after initiation)
- genotype-driven modification (change in ART regimen from initiation due to HIV genotype indicating insufficient potency of initial regimen)

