Patients recruited from the Johns Hopkins ED and/or JGBSP clinic social work will complete his/her ED/social work visit and will then be seen in the JGBSP clinic by a JGBSP clinic clinician for a medical HIV intake visit and prescription with receipt of ART starter pack. Patients recruited from the BCHD STD clinics will see be seen in the BCHD STD by a clinician for medical intake visit and prescription and receipt of ART starter pack. The clinicians who evaluate patients and initiate treatment will be those who provide continuity HIV care in the clinics. The date and time of the medical visit to initiate treatment at JGBSP clinic and BCHD STD clinic will be as soon as possible and the visit may occur as soon as immediately after recruitment (which is preferable) or may occur on a day other than the day of recruitment if the initial encounter occurs while the clinic is closed, is too late in the day to complete before clinic closes or patient prefers an appointment at a later date. The medical intake will take place no more than one week after consent is obtained. The intake will be as per usual in the JGBSP and BCHD HIV clinics. The following clinical labs will be obtained at the time of enrollment, as part of standard of care: CD4 count, HIV viral load, HIV genotype, CBC, comprehensive metabolic panel, urinalysis, viral hepatitis, syphilis serologies, GC/CT screening based on risk. As part of standard of care, clinicians and/or clinic staff (registered nurse, pharmacist) provide counseling on medication education, potential side effects and adherence. ART prescriptions will be written for at least 14 days of an antiretroviral medication regimen chosen at the discretion of the prescribing provider. Prescriptions for more than 14 days of medication can be prescribed at the discretion of the prescribing provider. Providers in the JGBSP and BCHD HIV clinics have expertise in prescribing antiretroviral medications and caring for HIV-infected patients and they will take into consideration adverse drug-drug interactions with other patient medications and patient comorbidities when choosing the starter pack of antiretroviral medications as per standard of care. Providers will also educate patients about the antiretroviral regimen and dosing recommendations as per standard of care. Pill boxes will be offered with each starter pack. At each clinic, patients are provided with 24/7 clinic contact information should he/she experience adverse side effects to medication and/or experience a medical emergency. Prescribing providers are responsible for reviewing the laboratory results and will follow up with the patient on any regarding any abnormalities requiring urgent/emergent medical attention including need to discontinue antiretroviral medication due to contraindications to a component in the regimen such as estimated creatinine clearance <30 mL/min (a contraindication with tenofovir alafenamide) or due to HIV resistance to a component of the antiretroviral regimen. Medical follow up will be scheduled within two to four weeks.

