#### Exclusion Criteria:

- Women who are currently pregnant or planning on becoming pregnant
- Adults lacking the capacity to consent
- Patients referred to HIV care outside of Johns Hopkins and/or BCHD STD clinics
- Patients with estimated creatinine clearance <30 mL/min at last documented laboratory testing in the available medical record at site of referral, self-report of

chronic kidney disease without documented creatinine within the last three months

- Patients judged by clinic or study staff to be physically or emotionally unable to provide consent or participate in all study procedures

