### **HIV linkage and care outcomes (Appendix 2):**

- number of referrals to linkage team
- number of patients who accept linkage services
- number of patients who complete initial HIV clinic appointment and time to appointment completion
- number of patients started on ART
- number of patients who achieve an undetectable HIV viral load time to ART initiation and time to achieve undetectable HIV viral load (<200 copies)
- baseline creatinine
- baseline genotype
- number of patients remain on ART through the end of the study
- number of patients who achieve an undetectable HIV viral load, time to ART initiation
- time to achieve undetectable HIV viral load (<200 copies)

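### Do the safety outcomes need a separate line for ART stopped or changed because of a contraindication found on baseline laboratory tests?

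*Protocol*

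**What the plan says.** In Section 1, on implementing rapid treatment initiation, baseline laboratory tests are drawn at the start: "The following clinical labs will be obtained at the time of enrollment, as part of standard of care". The prescriber then reviews the results. Among the matters needing urgent follow-up the protocol lists the "need to discontinue antiretroviral medication due to contraindications to a component in the regimen such as estimated creatinine clearance <30 mL/min", and then "or due to HIV resistance to a component of the antiretroviral regimen".

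The renal exclusion in Section 2 relies on existing information: "Patients with estimated creatinine clearance <30 mL/min at last documented laboratory testing in the available medical record at site of referral". It also excludes patients who report chronic kidney disease and have no creatinine on file from the last three months.

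Section 4 lists three safety outcomes under a heading that refers to Appendix 2. They are ART toxicity, which is not defined further; "ART simplification (change in ART regimen from initiation to ART regimen with fewer pills after initiation"; and "genotype-driven modification (change in ART regimen from initiation due to HIV genotype indicating insufficient potency of initial regimen". The linkage and care outcomes, which refer to the same appendix, include "baseline creatinine" and "number of patients remain on ART through the end of the study". Section 1 provides for chart review of linkage and care outcomes for 48 weeks after enrollment.

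**The concern.** Rapid initiation uses approved drugs and changes only how soon they are started. Its particular safety question is therefore what happens when treatment begins before the laboratory results are back. The protocol itself names two such consequences, and its outcome list gives only one of them a line.

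The missing event can occur. A patient with no creatinine on file and no known kidney disease passes the renal exclusion, may receive a starter pack at once, and may only later prove to have a contraindication. If the regimen is then switched, the participant still counts as remaining on ART. If the new regimen happens to have fewer pills, the change also meets the definition of simplification, which states no reason for the change. The report could then say how often genotype forced a change, but not how often another baseline result did.

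**Working it through.** No figure in the protocol bears on this point, so there is none to reproduce. The check sets the sections side by side.

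**1. Reasons, risks and outcomes.**

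| Reason for stopping or changing ART | Foreseen at laboratory review (Section 1) | Medical risk (Section 5) | Safety outcome (Section 4) |
|---|---|---|---|
| Resistance | Yes | Yes | Genotype-driven modification |
| Contraindication to a component | Yes | Not named | None by name |
| Side effects or toxicity | Not one of the two reasons given | Yes | ART toxicity |

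Of the two reasons in Section 1, one has a matching safety outcome. Of the two medical risks in Section 5, both have one. The list follows the protocol's own risk statement; it does not mirror every clinical reason for stopping.

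**2. Could another listed item hold the event?** Toxicity is undefined in the text available, so a contraindication-driven stop might be coded there, although a condition present before the first dose is not naturally drug toxicity. Simplification would catch a switch only if the pill count fell. Continuation on ART would show a permanent stop but not its reason. No listed item is a clean fit.

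**3. Could the event be found anyway?** Baseline creatinine is extracted, and it bears directly on the one contraindication that Section 1 gives as an example. Continuation on ART is extracted too, and the chart is the data source. In a sample this small, a low baseline value followed by a stop or switch can be looked up case by case. A contraindication of another kind would need a recorded reason for change. Appendix 2 may hold such a field, but it cannot be checked here.

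**4. Size.** Section 1 projects 32 participants. Section 4 has 32 patients identified and a participation rate of 67%, which implies 0.67 × 32 = 21.4, or about 21 enrolled (an inference; the protocol does not print this number). One affected participant is then 1/32 = 3.1% or 1/21 = 4.8%. The protocol gives no rate for unrecorded contraindications, so no probability of seeing one can be derived from it.

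**5. What depends on the count.** The stated purpose in Section 1 is to explore feasibility and acceptability. The protocol sets no safety hypothesis, comparison, threshold or stopping rule that uses the safety list. Every listed outcome can be counted as defined whether or not a fourth line exists.

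**The case for a change.** The strongest case for a change is that Section 4 fixes the safety list and defines two of its three items. The omission is then a matter of what the protocol specifies, not of analysis detail left for later. The event arises directly from starting before results are known, the protocol anticipates it, and one more line drawn from the existing chart review would cost almost nothing.

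Part of this stands. The mapping is right, and a report that also counted non-genotype laboratory reasons would tell the reader slightly more. Two parts do not carry the argument. A switched participant counting as still on ART is no defect, because that outcome measures persistence and a genotype-driven switch counts in the same way. The overlap with simplification needs a contraindication-driven switch that also lowers the pill count, which is too contrived a case to justify redefining that outcome.

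**Conclusion.** No change to the plan is needed. Section 1 describes the prescriber's clinical duty and Section 4 lists research outcomes. The second need not repeat the first, and neither contradicts the other. The toxicity and genotype outcomes match the risks in Section 5, and following the list as written leaves each outcome and the study's conclusions sound.

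What remains is a gap in reporting detail, worth 3.1% to 4.8% of the sample for each affected participant, at an unknown and unstated frequency. Analysts would sensibly fill it by noting, from the chart, any initial regimen stopped or changed because of a baseline laboratory result other than genotype.

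This rests on two assumptions: that the chart review gives access to regimen changes and the reasons for them, whether or not Appendix 2 has a dedicated field, and that the study is read as a feasibility and acceptability study. If the safety list were used to support a formal claim that starting before results is safe, the missing count would matter more.

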### *Sample Size and Analysis*

Based on 2015 data, we estimate identification of 32 newly diagnosed and previously diagnosed patients not in care during the 4-month study enrollment period. Assuming a participation rate of 67%, we will be able to enroll newly diagnosed patients and previously diagnosed patients not in care.

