## 1. Study Procedures

The study will enroll for a total of 12 months. Projected enrollment is 32 newly diagnosed patients and previously diagnosed patients not in care. As of May 8, 2017 the Moore clinic HIV practice will be incorporated into a new clinic, the John G. Bartlett Specialty Practice (JGBSP). Throughout the rest of this protocol, activities related to this practice will be referenced as the JGBSP clinic.

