### *Patient recruitment*

We will utilize existing HIV linkage to care services for newly and previously diagnosed patients identified at the Johns Hopkins East Baltimore campus, the JGBSP clinic and at the BCHD STD clinics to explore the feasibility and acceptability of RHTI in these settings. All patients identified in the Hopkins ED, Johns Hopkins inpatient HIV service, the JGBSP clinic and BCHD STD clinics who are newly diagnosed with HIV (test positive by 3rd or 4th generation HIV test or detectable HIV viral load with no previously documented positive HIV test by medical record and/or self-report) and patients with previous HIV diagnosis but by self-report are not in care and not on ART (> six months without HIV care and ART) will be referred to the Rapid HIV treatment initiation, Access and Engagement in care (RHAE) Research Assistant (RA) by call or text to a dedicated smart phone. At the time they are identified as needing a referral for HIV treatment services, a brief description of the study will be given to potentially eligible patients and a referral to the RHAE RA will be made with patient permission. In the ED, this referral will be made by ED HIV testing team members and/or ED clinicians. In the JGBSP clinic, the referral will be made by social work staff, nurses and/or medical providers. In the BCHD STD clinics, referrals will be made by patient advocates and/or medical providers. The linkage team will provide linkage services as per usual. In situations when potentially eligible patients present for clinical care when a Project RHAE staff member is not available to accept a referral and/or leave the clinical area before learning about the study, referring providers and staff who engage with the patient for treatment after the initial interaction will present the study and elicit interest and permission for referral at a later date in person or by phone. This may include patients who have been hospitalized at Johns Hopkins Hospital in which case the study team will discuss potential enrollment with the inpatient care team prior to approaching the patient for consent.

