#### *Electronic medical record data extraction*

HIV linkage and care outcomes will be collected for 48 weeks after enrollment and conducted through chart review of the electronic medical record at each site (Appendix 2). Data will be entered in REDCap Database by RHAE RAs through a tablet.

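### The protocol gives two enrolment periods (12 and 4 months) and uses 32 both as the number enrolled and as the number identified before 67% participation; its own inputs give about 21 enrolled, not 32

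*Protocol*

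**What the plan says.** Section 1, Study Procedures, opens with the recruitment plan: "The study will enroll for a total of 12 months. Projected enrollment is 32 newly diagnosed patients and previously diagnosed patients not in care".

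Section 4, under Sample Size and Analysis, is the only place where the number is derived. Working from 2015 data, it says "we estimate identification of 32 newly diagnosed and previously diagnosed patients not in care during the 4-month study enrollment period". It continues with "Assuming a participation rate of 67" per cent and a statement that patients will be enrolled. In the copy at hand no number enrolled appears in that last sentence. The number may have been lost from the copy, so its absence is not counted as an error.

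Three other places give context but do not settle the matter. The Patient recruitment text says the aim is to "explore the feasibility and acceptability of RHTI in these settings". The outcome list in Section 4 includes counts such as "number of patients who achieve an undetectable HIV viral load". The section on electronic medical record data extraction says "HIV linkage and care outcomes will be collected for 48 weeks after enrollment".

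**The concern.** The two statements describe the same recruitment and disagree on two points.

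- **Period.** Section 1 gives 12 months and Section 4 gives 4 months, a threefold difference.
- **Meaning of 32.** In Section 1 it is the number enrolled. In Section 4 it is the number identified, before the loss to non-participation. With 67% participation it cannot be both.

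How many patients are found, how many take part and over what period are central planning figures in a study of feasibility and acceptability. As the text stands, a reader cannot tell whether 21 enrolled would meet the plan or fall a third short of it. The number also sets the precision of any proportion reported among enrolled patients. The period sets how long the study runs to its last chart review.

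**Working it through.** **Inputs**

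- Enrolment period: 12 months (Section 1) or 4 months (Section 4, Sample Size and Analysis).
- Projected number enrolled: 32 (Section 1).
- Number identified: 32, tied to the 4-month period (Section 4).
- Participation rate: 67% (Section 4).
- Chart follow-up: 48 weeks per patient (Section 1, Electronic medical record data extraction).

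The protocol gives no significance level, power or effect size for the number, so the only formula that applies is: enrolled = identified × participation rate.

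**Attempt to reproduce 32 enrolled**

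| Reading | Identified | Enrolled at 67% | Relative to 32 |
|---|---|---|---|
| Section 4 as written: 32 in 4 months | 32 | 32 × 0.67 = 21.4 | 21.44/32 = 0.67 |
| 32 taken as the 12-month identified count | 32 | 32 × 0.67 = 21.4 | 0.67 |
| Assumption: Section 4 rate holds for 12 months (32/4 = 8 per month; 8 × 12 = 96) | 96 | 96 × 0.67 = 64.3 | 64.3/32 = 2.01 |

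None gives 32.

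**What 32 enrolled would require**

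- At 67% participation: 32/0.67 = 47.8, about 48 identified. At 8 per month that takes 48/8 = 6 months, which is neither stated period. Spread over 12 months it is 48/12 = 4 per month, half the Section 4 rate.
- With 32 identified: 100% participation.
- With 96 identified: 32/96 = 33% participation.

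The protocol states none of these.

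**Consequence for precision**

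The protocol gives no expected proportions, so two values are assumed here. The 95% confidence interval half-width by the normal approximation is 1.96 × √(p(1−p)/n).

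| Assumed p | n = 21 | n = 32 | n = 64 |
|---|---|---|---|
| 50% | ±21 points | ±17 | ±12 |
| 80% | ±17 | ±14 | ±10 |

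At n = 21 and p = 80%, only about 4 patients without the event are expected (21 × 0.2 = 4.2). The approximation is rough there and the figure is only a guide.

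**Consequence for study length**

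- 4 months ≈ 17.4 weeks; 17.4 + 48 = 65.4, about 65 weeks from first enrolment to last chart review.
- 12 months ≈ 52.2 weeks; 52.2 + 48 = 100.2, about 100 weeks.

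Follow-up per patient is 48 weeks in both cases.

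**The case against.** The strongest reply is that the Section 4 text is simply out of date. Section 1 speaks of a total of 12 months and carries the May 2017 change of clinic, so enrolment may have been lengthened there without an update to the derivation. On that reading this is a lapse in consistency more than a faulty calculation. It is plausible, but the protocol does not say so. If it is true, the only justification of the sample size is obsolete and still needs rewriting.

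Three further points deserve weight.

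- The figure of about 64 is a scenario. It needs a constant identification rate over 12 months, which the protocol does not state. Only about 21 follows directly. This stands, and 64 should be read as conditional.
- The number enrolled is missing from the end of the derivation in this copy, so 21 is computed here and not read from the protocol. This also stands. Restoring a number would not remove the conflict over 4 and 12 months, or over identified and enrolled.
- The practical effect is modest. The protocol lists descriptive counts and times, sets no precision target, and several outcomes (patients offered the intervention, patients referred) are not counted among the enrolled. Between n = 21 and n = 32 the half-widths differ by only 3 to 4 points. This limits the severity of the point but does not remove the contradiction.

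**Conclusion.** The concern holds. The current text gives two enrolment periods and two meanings for 32, and no other part of the protocol reconciles them. The derivation as stated yields about 21 enrolled, one third below the 32 in Section 1. If its monthly rate is assumed to continue for 12 months it yields about 64, twice that figure. Since the protocol does not show which period is current, it is open whether the true projection lies below or above 32.

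No decision rule changes, because no test, power or success threshold rests on the number. What is affected is the stated sample size, the precision of proportions among enrolled patients, and the length of the study (about 65 or about 100 weeks). This should be fixed, but it does not threaten the design.

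**What to change.** 1. State one enrolment period in both Section 1 and Section 4.
2. In Sample Size and Analysis, give the number expected to be identified in that period from the site data, apply the 67% participation rate, and state the resulting number enrolled.
3. Restate projected enrolment in Section 1 as that result. If 32 is the number identified in the chosen period, this is about 21.
4. If 32 enrolled is to stay, show an identified number and a participation rate, supported by the sponsor's data, that produce it. At 67% this means about 48 identified.

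The cost is wording in two places and a check of the 2015 data already used for the estimate. No visit or procedure changes. The projected enrolment may move up or down depending on the period the sponsor confirms.

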### **5. Risks**

Medical risks include side effects and/or toxicity to antiretroviral medication and need to change the antiretroviral regimen due to identification of HIV resistance mutations that preclude the use

of the antiretroviral medication regimen chosen by the prescribing provider. These risks, however, are not outside of the usual risks that come with initiating antiretroviral therapy. The major risks for participants are (a) discomfort in answering survey questions and (b) loss of privacy or confidentiality. In order to minimize the risks associated with discomfort in answering survey questions, participants will be told that they have the option to pass on any questions. In order to minimize the risks associated with loss of confidentiality, all participant data will be kept confidential and secure. All computers with participant data will be password protected with access restricted to certain study team members. No information will be kept on mobile devices, such as laptop computers or cell phones, unless such devices are encrypted and password-protected.

The Principal Investigator will assume responsibility for reporting any unanticipated problems or study deviations to the IRB.

## **6. Benefits**

There are no individual benefits for any study participants. However, participation in the study could show that initiation of ART in HIV positive patients at the time of diagnosis or when identified as previously diagnosed with HIV but not in care and antiretroviral naïve or off of ART for more than six months can improve clinical outcomes and decrease the risk of transmission of HIV.

## **7. Payment and Remuneration**

Study participants will receive \$25 for enrollment and completion of the baseline visit and \$50 at week 4 for completion of the standardized survey

